3.1.1. Methotrexate

All methotrexate doses **will be taken once per week in a divided dose**, one dose taken in the morning and one in the evening. Patients on methotrexate will be instructed to take their medication with food. For the first two weeks, an introductory dose of 15 mg/week (7.5mg BID once a week) orally will be administered to assess tolerability. This means taking 3 pills in the morning and 3 pills in the evening once a week. Patients should be instructed at the Enrollment/Baseline visit to begin methotrexate on a day that is convenient for them, within 6 days of enrollment. After two weeks, the dose will be increased to 25 mg/week (12.5mg BID) This means taking 5 pills in the morning and 5 pills in the evening once a week, until the end of follow-up or until treatment failure due to intolerability, adverse events, or of lack of efficacy.

If there are tolerability issues in the first two weeks such that the patient is not able to increase the dose, and unwilling to continue the current dose, treatment failure due to intolerability should be declared. The patient would then be eligible to switch treatment in Phase II. If this occurs in Phase II, treatment failure would be declared and patient will be treated according to best medical judgment. If the dose is increased per protocol at two weeks, the study ophthalmologist can decide to reduce the maintenance dose if the patient experiences severe side effects.

3.1.1.a. Dose Reduction MTX

If the patient is experiencing intolerable side effects, the study coordinator and patient will speak to the doctor about the possibility of a dose reduction, without revealing the name of the medication or the dosing instructions. The study doctor will then decide if the dose reduction should be done and inform the study coordinator and patient. The study coordinator will then provide the patient with new dosing instructions, away from sight of study physician. A dose reduction is not mandatory but is encouraged in the setting of intolerability.

For the first dose reduction, methotrexate will be reduced to 20 mg/week (10mg BID, once a week). This means taking 4 pills in the morning and 4 pills in the evening once a week. If side effects persist and the study ophthalmologist wishes to reduce the dose a second time, the dose will be reduced to 15mg/week (7.5mg BID, once a week). This means taking 3 pills in the morning and 3 pills in the evening, once a week. After the second dose reduction, treatment can be stopped if intolerability persists and the patient can switch to Phase II.

Although dose reductions are strongly encouraged, they **are not mandatory to attempt before determining treatment failure**. Treatment failure due to intolerability can be declared without trial of a dose reduction.

If a dose reduction has been utilized, and the investigator feels that the tolerability/safety issues have been resolved, it is at their discretion to return the patient to the maintenance dose level of the medication.

3.1.2. Mycophenolate Mofetil

Mycophenolate mofetil **will be taken twice daily**. Patients on mycophenolate mofetil will be instructed to take their medication on an empty stomach with no food one hour before or after taking each dose. For the first two weeks, an introductory dose of 500 mg BID orally will be administered to assess tolerability. This means taking one pill in the morning and one pill in the evening. After two weeks, the dose will be increased to 1.5 g BID. This means taking 3 pills in the morning and 3 pills in the evening until the end of follow-up or until treatment failure due to intolerability, adverse events, or lack of efficacy.

If there are tolerability issues in the first two weeks such that the patient is not able to increase the dose, and also is unwilling to continue, treatment failure due to intolerability should be declared. The patient would then be eligible to switch treatment in Phase II. If this occurs in Phase II, treatment failure would be declared. If the dose is increased per protocol at two weeks, the study ophthalmologist can decide to reduce the maintenance dose if the patient experiences severe side effects.

At any point if treatment failure is declared due to tolerability, the patient should be treated according to best medical judgment and still be followed up to their 6th month assessment (Phase I and Phase II).

3.1.2.a. Dose Reduction Mycophenolate Mofetil

If the patient is experiencing intolerable side effects, the study coordinator and patient will speak to the doctor about the possibility of a dose reduction, without revealing the name of the medication or the dosing instructions. The study doctor will then decide if the dose reduction should be done and inform the study coordinator and patient. The study coordinator will then provide the patient with new dosing instructions, away from sight of study physician. A dose reduction is not mandatory but is encouraged in the setting of intolerability.

For the first dose reduction, mycophenolate will be reduced to 1g BID. This means taking 2 pills in the morning and 2 pills in the evening. If side effects persist and the study ophthalmologist wishes to reduce the dose a second time, the dose will be reduced to 500 mg BID. This means taking 1 pill in the morning and 1 pill in the evening. After the second dose reduction, treatment can be stopped if intolerability persists and the patient can switch to Phase II.

Although dose reductions are strongly encouraged, they **are not mandatory to attempt before determining treatment failure**. Treatment failure due to intolerability can be declared without trial of a dose reduction.

If a dose reduction has been utilized, and the investigator feels that the tolerability/safety issues have been resolved, it is at their discretion to return the patient to the maintenance dose level of the medication.

3.1.2.b. Proton Pump Inhibitors and Mycophenolate Mofetil

Upon entering the trial some patients may be taking proton pump inhibitors (e.g. omeprazole). Due to a potential interaction with mycophenolate mofetil, H2 blockers are preferred over proton pump inhibitors. However, proton pump inhibitors are acceptable if the physician and/or patient does not want to change. This should be noted on the Baseline History Form under current systemic medications.

3.1.3. Folic acid

It is standard of care to prescribe folic acid supplements to reduce the severity of side effects in patients treated with methotrexate. All patients randomized to methotrexate will be prescribed 1mg per day of folic acid. It is fine to take folic acid the day methotrexate is taken.

3.1.4. Packaging and distribution of study medications

Patient medications will be purchased and packaged by [REDACTED], printed with the medication name, lot number, and expiration date. [REDACTED] will be responsible for distributing medications and labels with dosage instructions to all other sites.

Initial dose bottles will contain 14 days of medication at the lower initial dose. The initial two-week supply of methotrexate is 12 pills, and the initial two-week supply for mycophenolate mofetil is 28 pills. Maintenance dose bottles will contain 30 days' worth of medication, plus additional pills as a buffer for visit scheduling. Methotrexate maintenance dose bottles will contain 50 pills each. Mycophenolate mofetil maintenance doses will be provided in bottles of 100 pills each.

At the patient's first visit (i.e. Baseline for Phase I) they will be given the 14 day introductory dose and either one maintenance dose bottle of mycophenolate (100 pills) or one maintenance dose bottle of methotrexate (50 pills). At every monthly visit following, patients will be given an additional 30 days' worth of medication (50 pills of methotrexate, or 200 pills of mycophenolate) until 5 months. If a patient needs to schedule their appointment beyond the visit window allowed by the medication supply, additional bottles may be dispensed to ensure sufficient supply of medicine, although this scheduling should be discouraged.

If patients enter Phase II after treatment failure in Phase I, patients' medication will be dispensed following the same schedule as in Phase I. If patients enter Phase I (6-12 months) after treatment success in Phase I (0-6 months), they will be given 120 days' worth of medication at their 6 month visit. Lost bottles will be replaced.

Study medications, labeled with the appropriate dosing instructions, will be distributed to the study coordinator prior to each study visit. After randomization, before the drug is dispensed, the study coordinator will place the Study ID label on the bottles. If a dose reduction is used, the study coordinator will put a label on the bottle with the new instructions.

Study coordinators will also place number labels, provided by the coordinating center, on all bottles in order to track which individual bottles were dispensed to patients. Study coordinators will indicate on the Medication Log, what type of bottle they have dispensed (i.e. initial or maintenance), how many bottles, what type of bottle has been returned, and the numbers of the bottles.

If at any time the patient fails to bring in their used maintenance bottles, the study coordinator should refer to the clinic staff member responsible for maintaining the randomization list to verify patient assignment. This will ensure that the patient is given the correct maintenance bottle corresponding to their assignment.

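### One mycophenolate maintenance bottle lasts 16.7 days, not the stated 30 plus buffer, so default baseline supply can run out up to 14.8 days before an in-window Month 1 visit in that arm only

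*Combined protocol and SAP*

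**What the plan says.** Protocol section 3.1.4 describes maintenance bottles, without distinguishing the arms, as holding 30 days' "worth of medication, plus additional pills as a buffer for visit scheduling". Methotrexate bottles contain 50 pills, and for the other arm "Mycophenolate mofetil maintenance doses will be provided in bottles of 100 pills each".

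At baseline each patient receives the 14-day introductory supply and "either one maintenance dose bottle of mycophenolate (100 pills) or one maintenance dose bottle of methotrexate (50 pills"). At each later monthly visit up to Month 5 the patient receives a further 30 days' supply, given as "50 pills of methotrexate, or 200 pills of mycophenolate". For appointments booked later than the supply allows, "additional bottles may be dispensed to ensure sufficient supply of medicine", although the same sentence discourages such scheduling. For patients who switch drugs in Phase II, "medication will be dispensed following the same schedule as in Phase I".

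The maintenance doses are in sections 3.1.1 and 3.1.2. For methotrexate: "This means taking 5 pills in the morning and 5 pills in the evening once a week". For mycophenolate: "This means taking 3 pills in the morning and 3 pills in the evening until the end of follow-up". Table 9 (section 4.1.1) gives Months 1 to 5 a window of 15 days either side and Month 6 a window of 15 days before to 30 days after. Its note schedules visits by an average month length.

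**The concern.** The general statement about bottle content cannot hold for both drugs at these pill counts. Section 3.1.4 also contradicts itself: one 100-pill mycophenolate bottle is described as more than 30 days of drug, yet the monthly quantity called 30 days is 200 pills, which is two bottles.

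The slip reaches patients because only one bottle is dispensed at baseline. If mycophenolate runs out inside the Month 1 window and methotrexate does not, the plan builds in a possible treatment gap in one arm of a two-drug comparison. The gap would fall at about days 31 to 45, largely before the 6 to 8 weeks that section 3.2.1 allows for full drug effect, and while prednisone is being tapered.

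**Working it through.** **Inputs.** Mycophenolate: 2 pills a day for 14 days (28 pills), then 6 a day. Methotrexate: 6 pills a week for 2 weeks (12 pills), then 10 a week. Bottle sizes, dispensing and visit windows are as above. The protocol gives no figure for the average month; I assume 365.25/12 = 30.44 days. Days are counted from baseline. Results come from unrounded values.

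**The stated bottle content.**
- Methotrexate: 50/10 = 5 weeks = 35 days. This reproduces 30 days plus a buffer.
- Mycophenolate: 100/6 = 16.7 days. This does not. Two bottles would: 200/6 = 33.3 days. A single bottle would need 30 × 6 = 180 pills for 30 days with no buffer.

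**Baseline to Month 1.** All of this drug is dispensed at baseline, so no assumption about leftover pills is needed.
- Mycophenolate supply ends on day 14 + 16.7 = 30.7.
- Methotrexate supply ends on day 14 + 35 = 49.
- On the target date (day 30.4), mycophenolate has 0.2 days to spare and methotrexate 18.6.
- On the last in-window day (30.4 + 15 = 45.4), mycophenolate is 14.8 days short and methotrexate has 3.6 days to spare.
- With a 30-day month the last day is 45 and the mycophenolate shortfall is 14.3 days.

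**Later visits, assuming leftover pills are kept.** Supply before Month k lasts to 14 + 100/6 + (k − 1) × 200/6 days for mycophenolate and 49 + (k − 1) × 35 days for methotrexate.

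| Visit | Last in-window day | Mycophenolate lasts to | Shortfall (days) | Methotrexate lasts to |
|---|---|---|---|---|
| Month 1 | 45.4 | 30.7 | 14.8 | 49 |
| Month 2 | 75.9 | 64.0 | 11.9 | 84 |
| Month 3 | 106.3 | 97.3 | 9.0 | 119 |
| Month 4 | 136.8 | 130.7 | 6.1 | 154 |
| Month 5 | 167.2 | 164.0 | 3.2 | 189 |
| Month 6 | 212.6 | 197.3 | 15.3 | 224 |

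These shortfalls are alternatives and do not add up. A gap pushes the remaining supply later by the same number of days, so a patient's total time without drug is the largest shortfall so far, at most 15.3 days by Month 6. A patient seen on the last day of every window has gaps of 14.8, 0, 0, 0, 0 and 0.5 days. Pills supplied by then are 28 + 100 + 5 × 200 = 1,128, against 28 + 6 × (212.6 − 14) ≈ 1,220 needed, or 92%. For patients seen on target dates, mycophenolate slack is 0.2, 3.1, 6.0, 8.9, 11.8 and 14.7 days.

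**Later visits, if leftover pills are not kept.** With the previous visit on target, both arms fall short at the end of the window: 12.1 days (mycophenolate) and 10.4 (methotrexate) at Months 2 to 5, and 27.1 and 25.4 at Month 6. Only Month 1 then differs materially between arms.

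**Where the Month 1 gap falls.** Table 6, assuming a 60 mg start (lighter patients start lower), puts prednisone over days 31 to 45 at 35 falling to 25 mg/day after a 2-week initial hold, or 50 falling to 35 mg/day after a 4-week hold.

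**The case against.** The strongest reply is that the incorrect sentence does not govern dispensing. The explicit pill counts do, and they cover every visit held on its target date. The plan also foresees late visits and permits extra bottles. The Week 2 visit, at days 11 to 17, comes before any shortfall, and section 3.3 lists dispensing a new bottle, where applicable, among study-visit tasks. Pill counts and scheduling of the next visit are routine. A 14.8-day gap needs full adherence at full dose, no extra bottle, and attendance on the last permitted day; missed doses or a dose reduction stretch the supply. Finally, any Month 1 gap lies months before the Month 6 endpoint, and the protocol expects early flares and does not count them as failure.

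Much of this stands. The 14.8 days is a worst case, and no effect on the primary result has been shown. But the safeguards are optional. The extra-bottle provision concerns appointments knowingly booked late, so a patient who slips after Week 2 is not covered. A coordinator who believes that a bottle holds 30 days plus a buffer has no reason to add one. Because the same clause discourages booking beyond the supply, it in effect discourages mycophenolate Month 1 visits after day 31 that Table 9 permits, and no in-window methotrexate visit. Coverage on target dates does not answer the point either, because the buffer exists for visits off target.

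**Conclusion.** The concern holds. The bottle statement is wrong for mycophenolate by nearly a factor of two (16.7 days against 30 or more). By default the mycophenolate arm has almost no scheduling buffer before Month 1, and methotrexate is covered through the whole window. The worst case is 14.8 days without drug at Month 1. If leftovers are kept, no patient who attends the monthly visits can lose more than 15.3 days by Month 6. Phase II uses the same schedule and has the same weakness.

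These figures assume full adherence at the maintenance dose, no extra bottle and a 30.44-day month; a 30-day month changes the Month 1 gap by about half a day. The documents do not show how many patients would attend late, so neither the number affected nor the effect on Month 6 success can be estimated. The per-protocol set, which excludes patients taking less than half their drug, is not materially affected. This is an avoidable asymmetry between arms that should be corrected. It does not show that the primary comparison is biased.

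**What to change.** 1. At the baseline of Phase I and of Phase II, dispense two mycophenolate maintenance bottles (200 pills) instead of one. With leftovers kept, supply before Months 1 to 6 lasts to 14 + k × 200/6 = days 47.3, 80.7, 114.0, 147.3, 180.7 and 214.0. These pass the ends of the windows by 1.9, 4.8, 7.7, 10.6, 13.5 and 1.4 days.
2. Replace the general bottle statement with one for each drug: *one methotrexate bottle (50 pills) is 35 days of maintenance treatment; two mycophenolate bottles (200 pills) are 33.3 days*.
3. Turn the optional extra-bottle provision into a requirement in both arms: at each visit, staff confirm that pills in hand plus pills dispensed last to the end of the next visit window. This also covers sites where leftover pills are not kept.

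The cost is protocol wording and one extra 100-pill bottle per mycophenolate course, with somewhat more stock and more returned pills, including from patients who stop early. Doses, visits, endpoints and analyses do not change.

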3.1.5. Adherence to the treatment plan

Patients will be given a treatment diary in the form of a monthly calendar on which they will be asked to record the medications they are taking as well as reasons for missed doses. They will be asked to bring the calendars with them to each visit. Adherence will be monitored by the study coordinator through review of the calendars, and will be recorded on the Medication Log in each patient file. Pill counting of pills in bottles remaining from the previous study period will also be done for a more objective measure of adherence. If a patient has just started on a new bottle shortly before the visit, do not count these pills. For instance, if a patient returns for their two week visit two weeks plus two days after the baseline visit, the study coordinator will not count the pills remaining in the maintenance dose bottle they have just started on. If the patient fails to bring in their calendar, the study coordinator should ask the patient to estimate the number of doses they have missed.

3.1.5.a. Missed Doses

The following instructions will be given to the patients if they miss scheduled doses of their medication:

Methotrexate: If a patient misses their scheduled dose, they may take it the next day. If it is not taken the next day, they should wait until the following week. If patients make-up their dose on the next day, they should continue their medication weekly from the original day.

Mycophenolate Mofetil: If the patient misses a dose, they should continue with the regular dosing schedule.

3.2. Corticosteroid therapy

3.2.1. Oral prednisone

Prednisone vs. alternative oral corticosteroid

Unless contraindicated, oral prednisone should be used. An equivalent dose of an alternative oral corticosteroid may be used only if a specific contraindication to oral prednisone is present. All references to oral corticosteroid and specific dosing schedules presented in this Manual of Procedures are given for oral prednisone.

Initial dose

All patients enrolled in the study will be initially taking concomitant oral corticosteroids at 1 mg/kg or 60 mg daily, whichever is less. Treatment success is dependent upon successfully tapering concomitant prednisone to 7.5 mg/day. Initial corticosteroid dose will be continued for 2 to 4 weeks at which point prednisone will be gradually tapered.¹ Prednisone will be tapered to and held at 7.5 mg/day for the first 6 months of the study. Further reduction of corticosteroids will be allowed in Phase I after six months. If patients switch treatments and enter Phase II due to a failure of efficacy in Phase I, they will follow the same protocol as the initial Phase I corticosteroid

treatment and begin at 1 mg/kg or 60 mg, whichever is less. In patients failing for efficacy, investigators may start at a lower prednisone dose if they feel it is medically indicated. However, following the corticosteroid tapering guidelines is strongly encouraged. If patients switch treatments and enter Phase II due to a failure of intolerability in Phase I, then it is at the study doctor's discretion at what dose of corticosteroid to start the patient.

Tapering schedule

For all patients, oral prednisone will be tapered gradually according to Standardization of Uveitis Nomenclature (SUN) guidelines (see Table 6). As it takes 6-8 weeks for the study medications to take full effect, it is expected that inflammation may become uncontrolled with a corticosteroid taper in some patients during the first 3 months of the study. This does not necessarily mean that the randomized treatment has failed, since more time may be needed to ensure the drug has reached its full effect. If the study ophthalmologist believes that continued treatment is futile prior to the primary endpoint, treatment failure may be declared and the patient should enter Phase II. If this occurs in Phase II, treatment failure will be declared and the patient should be treated according to best medical judgment. However, all patients should be followed up to their 6th month assessment in Phase II.

At any point in Phase I or Phase II, investigators have the option of reducing the prednisone dose, and following a faster taper, if the patient is experiencing severe side effects. However, it is strongly encouraged that investigators follow the corticosteroid tapering guidelines. If **absolutely medically necessary**, the investigator may digress from the protocol and reduce steroids below 7.5 mg/day in the first six months, but this is strongly discouraged.

The corticosteroid tapering schedule for Phase I (6-12 months) is optional, and physicians may taper patients as they deem medically acceptable. It is not mandatory for patients to reduce down to 0mg of prednisone by 12 months. In general, a rapid taper in Phase I months 6-12 is not recommended due to issues of adrenal insufficiency.

Table 6: Tapering schedule for oral prednisone: Phase I or if starting new medication in Phase II*

Dose (mg/day)	Duration (weeks)	Decrement (mg/day)
60	2 – 4 ¹	10
50	1	10
40	1	5
35	1	5
30	1	5
25	1	5
20	1	2.5
17.5	1	2.5
15	1	2.5
12.5	1	2.5
10	1	2.5
7.5	hold*	

NOTE: Begin patients at 1mg/kg or 60 mg/day, whichever is less. For Phase I hold patients at 7.5 mg/day, up to the end of 6 months.

*If starting Phase II and failed Phase I due to efficacy.

If uveitis does not improve at the end of the first 4 weeks, use best medical judgment regarding supplemental treatment (e.g. pulse dose treatment, corticosteroid injections, additional immunosuppressives).

Table 7: Optional tapering schedule Phase I (6-12 months)

Dose (mg/day)	Duration (weeks)	Decrement (mg/day)
7.5	1*	2.5
< 7.5 & ≥ 5	2 – 4	1 - 2.5
< 5 & ≥ 2.5	2 - 4	1.5 - 2.5
< 2.5 & ≥ 1	2 – 4	1
0		

NOTE: When beginning Phase I (6-12 months), hold patient at 7.5 mg/day, for at least one week.

Directions for Rescue Taper

Reactivations can be mild or severe. Mild reactivations are considered an increase in inflammation up to the 1+ level in anterior chamber cell or vitreous haze. Severe reactivations are considered an increase in inflammation up to the 2+ level or higher in anterior chamber cell or vitreous haze. Retinal/choroidal lesions may be considered mild or severe at the discretion of the study physician.

If uveitis reactivates:

- Increase oral prednisone up to a dose of 1 mg/kg for severe reactivations, or for mild reactivations, up to double the dose at which the flare occurred, until uveitis is controlled. Then re-taper according to the guidelines.

Uveitis is considered non-responsive if inflammation does not increase but does not further improve after the first 4 weeks of treatment on 1mg/kg oral prednisone.

If uveitis is non-responsive:

- Hold the current dose of prednisone for an additional week. If still no improvement, treatment failure due to futility may be declared, and patients may proceed to Phase II. Alternatively, other therapies may be added, but these should be noted as a protocol deviation.
- If treatment failure is declared due to futility in Phase I, before the primary endpoint of 6 months, patients may switch to Phase II. Patients who refuse to switch to Phase II should be encouraged to return for a 6-month visit. Patients who switch to Phase II will already be followed.
- If treatment failure is declared due to futility in Phase II, before the primary endpoint of 6 months, patients will be treated according to best medical judgment. If treatment failure is declared prior to 6 months, Phase I and Phase II, every attempt must be made to bring patients back for their 6 month assessment.

After suppression of uveitis is once again achieved (either in the case of reactivation or non-response) follow the taper guidelines for Phase I. Patients who have failed the treatment to which they are randomized will then switch treatments, begin Phase II, and follow the same taper guidelines as Phase I (0-6 months). If patients flare during Phase II, they can follow directions for the rescue taper listed above. Patients who fail the second treatment at the 6 month endpoint will be treated as per the investigators discretion.

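### Above 0.5 mg/kg, the rescue rule allows more prednisone for a mild flare than for a severe one

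*Combined protocol and SAP*

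**What the plan says.** Protocol section 3.2.1, Directions for Rescue Taper, sorts reactivations by inflammation grade alone: "Mild reactivations are considered an increase in inflammation up to the 1+ level in anterior chamber cell or vitreous haze", and "Severe reactivations are considered an increase in inflammation up to the 2+ level or higher in anterior chamber cell or vitreous haze". Retinal and choroidal lesions are left to the physician's judgment. Neither definition depends on the prednisone dose being taken.

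The dose rule is one sentence: "Increase oral prednisone up to a dose of 1 mg/kg for severe reactivations, or for mild reactivations, up to double the dose" at the time of flare, continued until the uveitis is controlled. It is followed by "Then re-taper according to the guidelines". The same directions carry over to the second drug: "If patients flare during Phase II, they can follow directions for the rescue taper listed above".

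The 60 mg/day limit appears only where starting doses are set. Section 3.2.1, Initial dose, says "All patients enrolled in the study will be initially taking concomitant oral corticosteroids at 1 mg/kg or 60 mg daily, whichever is less", and the note under Table 6 says "Begin patients at 1mg/kg or 60 mg/day, whichever is less". The inclusion criteria in section 2.3.2 also mention 60 mg, again for starting treatment.

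**The concern.** A rescue rule graded by severity should allow at least as much treatment for the worse event. This one does so only at lower doses. Higher on the taper, doubling passes 1 mg/kg, and the patient with the milder flare has the higher ceiling. In a trial whose purpose is to spare corticosteroid, a site following the text could expose a patient with 1+ inflammation to a dose that the same sentence does not allow for 2+ or worse. The issue is patient safety and consistent conduct across sites. The rule is the same in both arms.

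**Working it through.** **Inputs from section 3.2.1.** Severe ceiling: 1 mg/kg, that is W mg/day at W kg. Mild ceiling: 2D, where D is the dose at flare. Starting dose: the lesser of W and 60 mg/day, held for 2 to 4 weeks. One-week steps in Table 6: 50, 40, 35, 30, 25, 20, 17.5, 15, 12.5 and 10 mg/day, then a hold at 7.5.

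**Assumptions.** The documents give no body weights, so 40 to 120 kg in 5 kg steps is used. A patient who starts below 60 mg/day is taken to join Table 6 at the next lower step.

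**Condition for reversal.** The mild ceiling exceeds the severe one when 2D > W, that is when D/W > 0.5 mg/kg. The gap is 2D − W. For example, at 60 kg with a flare at 50 mg/day, 2 × 50 − 60 = 40 mg/day.

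**First taper, one-week steps only.**

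| Weight (kg) | Steps that reverse (mg/day) | Gap, 2D − W (mg/day) | Weeks after a 2-week / 4-week hold |
|---|---|---|---|
| 40 | 35, 30, 25 | 30, 20, 10 | 3–5 / 5–7 |
| 45 | 40, 35, 30, 25 | 35, 25, 15, 5 | 3–6 / 5–8 |
| 50 | 40, 35, 30 | 30, 20, 10 | 3–5 / 5–7 |
| 55 | 50, 40, 35, 30 | 45, 25, 15, 5 | 3–6 / 5–8 |
| 60 | 50, 40, 35 | 40, 20, 10 | 3–5 / 5–7 |
| 65 | 50, 40, 35 | 35, 15, 5 | 3–5 / 5–7 |
| 70 | 50, 40 | 30, 10 | 3–4 / 5–6 |
| 75 | 50, 40 | 25, 5 | 3–4 / 5–6 |
| 80, 85, 90, 95 | 50 | 20, 15, 10, 5 (one per weight) | 3 / 5 |
| 100 or more | none | – | – |

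On these steps the gap is 5 to 45 mg/day at the tested weights. It stays under 50 mg/day at any weight from 40 kg up: the worst case is a weight just above 50 kg at the 50 mg step, where 100 − W is just under 50. At 20 mg/day or less, 2D is at most 40, so nothing reverses at 40 kg or more.

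**Flare at the starting dose during the initial hold.** The gap is 2 × min(W, 60) − W:

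- 45 kg: 90 − 45 = 45 mg/day
- 60 kg: 120 − 60 = 60 mg/day
- 80 kg: 120 − 80 = 40 mg/day
- 100 kg: 120 − 100 = 20 mg/day
- 120 kg: 120 − 120 = 0

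So a flare at this stage reverses for anyone under 120 kg. At 60 kg or less the starting dose is already 1 mg/kg: the severe rule permits no increase, while the mild rule permits 2 mg/kg.

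**Can a flare happen at these doses?** Section 3.2.1, Tapering schedule, expects some loss of control during the first 3 months, which covers all the weeks in the table. Re-tapering after a rescue can bring the higher doses back later than week 8, and the directions apply again in Phase II.

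**The case against.** The strongest reply is that no uveitis specialist would use the rule this way. Section 2.3.2 calls 1 mg/kg high-dose, and section 3.2.1 uses it as the starting limit, the severe rescue limit and the yardstick for non-response. It is the evident working maximum, and both limits are phrased as upper bounds. This lowers the practical risk, but it is an inference: no sentence applies that maximum to the mild rule.

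The initial-hold case is open to fair challenge. Patients enter with active disease, so inflammation that persists on the starting dose is more naturally non-response, which has its own instructions. A true reactivation there needs improvement and then a return to 1+ within 2 to 4 weeks on the full dose. The text does not exclude this, but the 60 mg/day gap belongs to an edge case and the one-week steps are the better guide.

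The note under Table 6 also allows pulse dosing, so the severe ceiling is not absolute. That allowance is for uveitis that has not improved after the first 4 weeks. It does not explain a higher ceiling for a mild flare.

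Finally, few scheduled visits fall in the affected weeks. That is true, although the Month 1 visit, with its window of ±15 days, falls in or next to them, and non-study visits can occur at any time.

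**Conclusion.** The concern holds, at low severity. As written, the mild ceiling exceeds the severe ceiling for every flare above 0.5 mg/kg. That threshold is exact and needs no assumption. Which taper steps are affected depends on the assumed weights and on the assumed entry point to Table 6 for patients starting below 60 mg/day. On those assumptions, at most four one-week steps reverse.

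The figures are differences between two permitted maxima, not estimates of dose received. The documents give no flare rate by dose, so the number of patients affected cannot be estimated.

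**What to change.** In section 3.2.1, Directions for Rescue Taper, add to the mild limit: *not to exceed 1 mg/kg (the ceiling for severe reactivations)*. At 60 kg with a flare at 50 mg/day, the mild maximum then falls from 100 to 60 mg/day, equal to the severe maximum. Flares at or below 0.5 mg/kg are handled as now.

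Above 0.5 mg/kg the two ceilings become equal, so the change removes the reversal without making the response graded. It also still allows more than 60 mg/day in heavier patients: a mild flare at 50 mg/day in a 100 kg patient could go to 100 mg/day. Whether rescue should also carry the 60 mg/day limit is a separate clinical choice.

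The cost is one clause and a site memo, with no extra data or patients.
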